2.5 PILOT TESTING

Prior to enrollment of the 100 participants, we will perform 2 pilot intervention groups; each will include 3 group sessions with approximately 5 participants each. The groups will be led by trained SCRIPT interventionists. The purpose of this pilot phase is to ensure that our intervention is culturally appropriate, feasible to conduct, and relevant to our participants. We will use feedback from the pilot study to make improvements to our study before we begin recruiting participants.

For the pilot phase of the study, we will recruit approximately 10 participants from the same study population as outlined above to conduct two pilot intervention group trainings. Thus, no control groups will be pilot tested. These pilot participants will receive the same study procedures as the main study participants (recruitment, screening, informed consent, baseline assessment, compensation, group sessions), except they will not receive the 1-month nor the 6-month assessments. The pilot participants will provide informed consent using a form that is specific to the pilot phase of the study. The study flyer and pamphlet will not be used for recruitment during the pilot phase. All data collected during this pilot phase will not be used for feasibility or intervention effectiveness analyses, but may be used for secondary analyses of baseline data.

2.6 STUDY SITES

Participants will be recruited through a civil society organization (CSO) providing street outreach services to PWID and people living with HIV in St. Petersburg, Russia. CSOs serving PWID and PLWH have been historically funded by the Global Fund; currently, they are financed mostly by foundations and private donations. All are closely monitored by the Russian authorities. They have no specific rules on medical privacy, other than providing an inviting, safe haven for affected people, who congregate at the CSOs for support and mutual help. The latter offer counseling, but usually have no medical staff and do not offer therapy.

All assessments and group trainings will be conducted at a rehabilitation center. Street outreach CSOs do not have facilities to conduct study procedures, but have connections with other organizations, such as rehabilitation centers, and thus participants recruited from the CSOs will be transported to these organizations for all other study procedures. The rehabilitation centers have the resources and capacity to conduct the assessments and intervention. Therefore, this collaboration with the CSOs is a multi-institutional approach to reach individuals in a highly stigmatized population and help them address the negativity in their lives related to other people's attitudes about their HIV status and substance use.

Recruitment will be completed by the CSO staff and phone-screening will be completed by the rehabilitation center staff, who are trained as research assessors (RAs) by academic staff at PMSU. In-person screening, informed consent, and assessments will also be completed by RAs. Intervention sessions will be completed by trained ACT interventionists on site at the rehabilitation center or at the Laboratory of Clinical Pharmacology of Addictions at the First St. Petersburg Pavlov State Medical University (PSMU) in St. Petersburg, Russia. PSMU is the major educational, scientific, and clinical medical institution for northwestern Russia. The ACT interventionists are both rehabilitation center staff and PMSU staff, who were trained in ACT for this study by the PI and master trainer consultants in a workshop modified for the Russian context, conducted from March 2 through March 9, 2019.

2.7 INCLUSION CRITERIA

To be eligible to participate in the trial, participants will need to meet the following inclusion criteria:

1. 18 years old or older
2. HIV-positive
3. Current injection drug use (past 30 days)
4. Not currently on ART
5. Provision of contact information for two contacts to assist with follow-up
6. Address within 100 kilometers of St. Petersburg
7. Not enrolled in any other research studies
8. Possession of a telephone (home or cell)
9. Able and willing to comply with all study protocols and procedures over 6 months
10. Available at the specific days of the week and times that the group sessions will be occurring for the subsequent 3-4 weeks (to ensure that participants randomized into the intervention arm will be able to receive the intervention)

2.8 EXCLUSION CRITERIA AT STUDY ENTRY

1. Not fluent in Russian
2. Cognitive impairment resulting in inability to provide informed consent based on research assessor (RA) assessment
3. Acute severe psychiatric illness as determined from screening questions (i.e., answered yes to any of the following: past three month active hallucinations; mental health symptoms prompting a visit to the ED or hospital; mental health medication changes due to worsening symptoms; presence of suicidal plans) and research assessor clinical observation (i.e. clinical observation or prior knowledge of severe personality disorder; past three months active mania; past three months active psychosis)
4. Participants in the main study did not participate in the pilot portion of the study.

2.9 RECRUITMENT GOALS

We aim to randomize 100 participants over 13 months into the trial. We will approach potential participants at CSOs serving PWID and people living with HIV (PLWH) in St. Petersburg.

3. INTERVENTION

3.1 INTERVENTION OVERVIEW

The study will randomize 100 PWID living with HIV in the St. Petersburg area. We will approach potential participants at CSOs serving PWID and people living with HIV (PLWH). After a phone-screening, potential participants will be given clear transportation instructions to the location of the remainder of the procedures (in-person screening, consent, enrollment, assessments, intervention sessions). After in-person screening, consent, enrollment, and the baseline assessment, participants will be randomly assigned to either the SCRIPT intervention or standard of care. Following randomization, participants in both groups will receive standard of care at the study site.

Following randomization by RAs at the rehabilitation center, participants in the intervention group will be scheduled to engage in group ACT sessions. These will consist of three 2-hour group sessions of culturally adapted ACT to reduce stigma and related manifestations in weeks 1, 2 and 3. The ACT sessions are described in further detail in 3.3.A.

Throughout the course of the study, participants will be expected to participate in three in-person assessments (baseline, 1 month [4 weeks], and 6 months [24 weeks]). Participants in the intervention groups will receive three ACT sessions over one month in approximately 13 groups of 5 people each (n=65), with a final assessment conducted at 6 months.

3.2 RANDOMIZATION

Randomization is not stratified by any factor. Blocked randomization with randomly selected block sizes was used to reduce selection bias and make the sequence less predictable. We generated a random sequence of 34 blocks, sizes 3 and 6. Then, we randomized assignments within each block with an allocation ratio of 2:1. A greater number of blocks was created than is necessary in the event that the investigator continues enrollment beyond the initially planned sample size. Randomization sequence was created in R, version 3.5.2 (Copyright (C) 2018 The R Foundation for Statistical Computing) and uploaded to REDCap platform, electronic data collection tool.

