9. STAFF TRAINING

9.1 TRAINING OF STUDY STAFF

All study staff will be trained on the study protocol. Training will take place in-person in Tbilisi, Georgia, St. Petersburg, Russia, and via webinars.

Recruitment will be performed by a CSO outreach worker who has extensive experience working with this population. In-person screening, enrollment, and all assessments will be performed by Research Assessors (RAs) who have experience working with this population. The staff are trained to assess for adverse events and will follow established protocols for identifying and monitoring any ongoing adverse events.

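### Section 3.2 prints both block sizes in the protocol used to train all staff, which makes about 10 of 100 allocations deducible with certainty by someone who has followed the whole sequence

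*Combined protocol and SAP*

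**What the plan says.** Section 3.2 gives the purpose of the method: "Blocked randomization with randomly selected block sizes was used to reduce selection bias and make the sequence less predictable". It then gives the details: "We generated a random sequence of 34 blocks, sizes 3 and 6", followed by "Then, we randomized assignments within each block with an allocation ratio of 2:1". There is a single sequence: "Randomization is not stratified by any factor". The list was loaded into REDCap. The target in Section 2.9 is 100 randomised.

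Section 9.1 says "All study staff will be trained on the study protocol", and gives in-person screening, enrolment and all assessments to the RAs. Section 2.8 makes the cognitive-impairment exclusion a judgement, "based on research assessor (RA) assessment". The psychiatric exclusion combines listed screening questions with RA clinical observation. Section 3.1 places allocation with the same staff: "Following randomization by RAs at the rehabilitation center".

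Nothing in the document withholds the block sizes from RAs or assigns them to a restricted file. Section 7.3 describes REDCap user privileges only in general terms.

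**The concern.** Varying the block size protects a sequence only while staff who enrol cannot tell where a block ends. Once the possible sizes are known, some runs of past allocations leave only one possibility for the next. Keeping the list in REDCap stops people reading it, but does not stop them deducing from what has already been allocated.

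The staff who could make that deduction also decide whether a candidate passes a judgement-based exclusion. If the next allocation is known before eligibility is settled, a candidate can be kept for or kept out of that slot. The arms may then differ at baseline, and analysis by randomised group does not repair selection that came before randomisation. The outcomes at stake are the between-arm comparisons in Aim 2, above all the two stigma scales at 1 month.

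**Working it through.** **Inputs.** Block sizes 3 and 6, 34 blocks, ratio 2:1, no stratification (Section 3.2); 100 participants (Section 2.9). The probability that a block has size 3 is not stated. I assume 0.5 and show 0.25 to 0.75.

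**The plan's own figure.** Section 3.2 says more blocks were created than needed. The minimum is 34 × 3 = 102 slots and the maximum 34 × 6 = 204. With equal chances the mean is 34 × 4.5 = 153. So 34 blocks always cover 100, and the figure is reproduced.

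**How certainty arises.** A block of 3 holds 2 ACT and 1 control; a block of 6 holds 4 and 2. Two examples from the start of the sequence:
- Control, control can only be a block of 6, so the next four are ACT.
- Four ACT in a row can only be a block of 6, so the next two are control.

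Whether a call is certain depends only on which sizes are possible. The mix affects how often such runs occur.

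**Hand check on fixed blocks.** Within a block, the certain allocations are the closing run of one arm.
- Size 3: the three orders CAA, ACA and AAC (A = ACT, C = control) give 2, 1 and 1 certain calls, a mean of 4/3 per block. The 33 full blocks in 100 give 33 × 4/3 = 44.
- Size 6: the expected closing run of ACT is 4/6 + (4·3)/(6·5) + (4·3·2)/(6·5·4) + (4·3·2·1)/(6·5·4·3) = 1.333. For control it is 2/6 + (2·1)/(6·5) = 0.400. The total is 1.733 per block. Sixteen full blocks give 27.7, and the four slots left over add 4/15 = 0.27, so about 28.

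The simulation below gives 44.1 and 28.1, which agrees.

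**Simulation.** 3,000 sequences of 100 per row (1,500 for the row allowing size 12). The observer sees every past allocation, knows the ratio and updates by Bayes' rule. A call is certain when the predicted probability of ACT is exactly 0 or 1.

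| True blocks; what the observer believes | Certain per 100 (ACT / control) | Best guess correct | Controls called correctly |
|---|---|---|---|
| 3/6 equally likely; knows 3/6 | 10.2 (8.0 / 2.1) | 75.5% | 35.2% |
| 3/6, P(size 3) = 0.25; knows this | 12.9 (10.2 / 2.8) | 74.8% | 35.8% |
| 3/6, P(size 3) = 0.75; knows this | 6.0 (4.7 / 1.3) | 76.2% | 34.1% |
| 3/6 equally likely; allows 3/6/9 | 0.0 | 75.5% | 35.3% |
| 3/6 equally likely; allows 3/6/9/12 | 0.0 | 75.4% | 35.3% |
| Fixed 3; known | 44.1 (33.0 / 11.1) | 77.7% | 33.2% |
| Fixed 6; known | 28.1 (21.7 / 6.4) | 74.2% | 26.0% |

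In the first row, the 5th to 95th percentile across trials is 3 to 18 certain allocations.

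**Reading the table.** Compare the first row with the fourth and fifth. Disclosure moves certain calls from 0 to about 10 per 100 and leaves the other two columns where they were. Allocations with a probability of ACT of 0.4 or less also change little: 14.6% with the sizes known, 12.9% or 12.1% without (separate run of 1,500 sequences).

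**The case against.** **Average guessability is not caused by disclosure.** A reader might set 75% correct guesses against the 66.7% obtained by always guessing ACT, and blame the printed sizes for the gap. That is wrong: the 75% is unchanged when the sizes are withheld. The gap measures 2:1 blocking. This objection stands in full, and only the certain calls can be charged to the sentence in Section 3.2.

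**Most certain calls are for the likelier arm.** About 8 of the 10 are ACT. An assessor who knows that control comes next would have about 2 such occasions per 100. This also stands. A certain ACT slot can be steered too, but the information gained is smaller.

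**The observer is idealised.** A reader might infer that each RA sees every allocation and decides when people are screened. The document says neither. Section 3.1 refers to RAs in the plural, and one who sees fewer allocations predicts less. Outreach staff recruit and start the phone screen (Sections 2.6 and 4.2), and the only deferral by RAs that is described is for people acutely ill or in withdrawal (Section 4.3). Section 3.2 is in the past tense, and the version used for training may not have carried the sentence. So the 10 per 100 applies to a fully informed observer and is not an estimate for a typical RA.

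**Some protection exists.** Varying the size helps: certain calls are about 10 per 100, against 44 or 28 with known fixed blocks. Allocation follows consent and baseline, so steering would have to happen at screening or enrolment.

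**No motive is stated.** That is true. Section 4.5 has the first session wait for five participants randomised to ACT, which gives staff a practical reason to notice the next slot. That link is my inference. The primary outcome of Aim 1, satisfaction, is asked only of the intervention group (Section 5.2), so steering cannot create a between-arm difference in it.

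**Conclusion.** The point holds as a small, avoidable weakness in allocation concealment. Printing the sizes partly undoes the purpose that Section 3.2 gives for varying them. For an observer who knows the sizes and the full history, it makes about 10 of 100 allocations certain (about 8 ACT, 2 control), with a range of about 6 to 13 over the assumed mixes.

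This rests on three assumptions: the unstated mix of sizes, a complete view of past allocations, and a comparison observer who keeps larger blocks in play. Someone who correctly guessed 3 and 6 unaided would gain little from the printed sentence.

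A reader might go further and infer that the arms were in fact selected, or that the sequence is broadly predictable because of this sentence. The document supports neither. It reports no exploitation, and average predictability is the same with or without disclosure.

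**What to change.** Move the block sizes and number of blocks from Section 3.2 to a restricted randomisation document that staff who screen, enrol or randomise cannot open. Leave in the protocol only that permuted blocks of varying size were used at 2:1. Add a sentence saying who holds the list and what an RA can see in REDCap before and after allocating a participant.

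Deleting the sentence does not remove knowledge already given. If RAs have the sizes and enrolment is still open, regenerate the unopened blocks with undisclosed sizes. If enrolment has closed, record in the report which staff had access to the sizes. The document does not give the enrolment status.

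The cost is small but not nil. The text change needs an amendment to both IRBs, since Section 6.2 sends all protocol changes to both. Regeneration adds a new list and a REDCap reload. Sample size, ratio and analysis are unaffected.

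The fix removes the certain calls only. The guessability that comes with 2:1 blocking remains.

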3.3 INTERVENTION

The SCRIPT intervention is comprised of a culturally adapted ACT intervention designed to reduce stigma and related manifestations. Both ACT and standard of care groups will receive the usual care at the CSO and study sites, which includes counseling and referral to addiction treatment clinics (for detox and rehabilitation; opioid agonist treatment is not available in Russia) and to HIV treatment clinics (for ART and HIV care) in St. Petersburg (standard of care).

3.3.A. ACCEPTANCE AND COMMITMENT THERAPY (ACT)

The ACT intervention will consist of three sessions scheduled for 2 hours each. Sessions will occur in groups of approximately 5 and will follow an intervention manual, based on the one developed in Luoma et al. (2008) and Luoma et al. (2012) and culturally adapted to a Russian context by the study team. Participants are told that the groups are intended to help them overcome stigmatization, shame and judgments of self and others. Standard ACT exercises are modified to focus on how to respond to shame and self-stigmatizing thoughts in a

way that would not obstruct recovery from SUD or health care seeking. In an ACT approach, rather than trying to reduce or eliminate manifestations of internalized stigma (such as shame), acceptance techniques encourage participants to notice these feelings and reduce their conditioned link to potentially adverse outcomes such as risk behaviors or avoidance of care.⁴⁹ The initial phase of the intervention focuses on the workability of suppression and avoidance, and provides a rationale for defusion and acceptance skills. Well known ACT exercises will be adapted as needed for the Russian cultural context in which this study is conducted. The intervention then proceeds to teach defusion and acceptance skills through such exercises as 30 seconds of word repetition focused on a negative self-judgment, a procedure known to reduce both fusion with thoughts and the distress they evoke (Masuda, Hayes, Sackett, & Twohig, 2004). This phase also includes mindfulness exercises, acting out a tug of war with a negative thought, and publicly sharing negative self-judgments by writing them on name tags. The third phase of the treatment focuses on helping participants identify life goals and values. They are guided to respond and refocus on actions related to their values, such as self-care activities that would reduce their HIV risks and support care seeking.¹⁰ It also includes a focus on building a positive agenda of human connection and values related to treatment participation. Finally, participants write out an epitaph for their life and share their values, goals, needed actions, and expected barriers. Follow up sessions will review this material with clients, as well as address barriers to implementing these skills in their lives. When speaking to participants, we will refer to ACT as Acceptance and Commitment Training, as the goal of the sessions is to *train* participants how to overcome stigmatization.

The ACT stigma intervention will be delivered by clinical psychologists. Supervision will be provided by site PI and ACT trainer. Interventionists and supervisors will be trained by ACT trainers and PI. To assess interventionist fidelity to ACT for quality assurance, we will use the Adherence Raters' Manual for Stigma Treatment Study (Kohlenberg et al, 2004) to rate the recorded intervention audio tapes, with a focus on interventionist behavior and competency. The measure classifies three different targets of clinician behaviors, openness, awareness, engagement, as well as interventionist stance. The coding will be conducted by an ACT clinician who is also a certified ACT trainer. This will also allow us to investigate how combinations of interventionist behaviors relate to outcomes and help train future interventionists in Russia and Russian speaking countries. Fidelity will be measured by an adherence checklist completed by interventionists after each session.

The ACT sessions will be scheduled to take place at the rehabilitation center. The First St. Petersburg Pavlov State Medical University is an alternative location where sessions can be conducted. Sessions will be planned to occur in a weekly succession, with a goal of 3 sessions within the first month of study participation.

The sessions will entail exercises on values, goal setting, psychological flexibility and commitment, led by an ACT-trained interventionist.

All sessions will be audio recorded for quality assurance purposes. The interventionist will use discretion to turn the recorder off if a participant feels uncomfortable disclosing certain sensitive information, in which case she will turn it back on as soon as appropriate. Audio recordings of intervention sessions will be deleted seven years after the completion of study analyses and publication of all study manuscripts.

Study participants will be invited to refer to each other by a nick name or pseudonym in the groups, however, participants can use their real first names, if preferred. Interventionists will instruct participants to not repeat anything they have heard in these sessions.

3.4 CONTROL GROUP

Participants in the control group will receive standard care as normally provided to patients by civil society organizations. This could include information on HIV and substance use disorders, counseling, referral to addiction treatment clinics, and referral to HIV treatment clinics. They might also be given printed information, including phone numbers, on places that provide HIV medical care and substance use treatment.

3.5 SCHEDULE OF DATA COLLECTION

		Phone Screener	Screener and Baseline		ACT Sessions 1-3	1-month assessment (4 weeks)	6 month visit (24 weeks)
			In-person Screener	Baseline			
Screening	Verification of HIV and hx of IDU	X	X				
	Screening Questions	X	X				
Enrollment	Sign Informed Consent		X				
	Complete contact information/verify numbers			X			
Assessment	Baseline Study Assessment			X			
	1-Month Study Assessment incl ACT satisfaction questions					X	
	6-Month Study Assessment						X
	Interventionist Checklist				X		
Randomization	Randomization			X			
Intervention	Adverse Events			X		X	
	ACT Intervention				X		
Other	Compensate for Participation			X	X	X	X
	Provide Resource Card			X			
	Report Adverse Events			X	X	X	X
	Complete Tracking Forms		X	X	X	X	X

Control Group						
		Phone Screener	Screener and Baseline Visit		1 mo (4 weeks)	6 mo (24 weeks)
			In-person Screener	Baseline		
Screening	Verification of HIV and substance use	X	X			
	Screening Questions	X	X			
Enrollment	Sign Informed Consent		X			
	Complete contact information/verify numbers			X		
Assessment	Baseline Study Assessment				X	
	1-Month Study Assessment					X
	6-Month Study Assessment					X
	Randomization				X	
Other	Provide Resource Card				X	
	Compensate for Participation				X	X

	Complete Tracking Forms			X	X	X
--	-------------------------	--	--	---	---	---

3.5.A. VISIT WINDOWS

ACT Intervention Session Windows for Intervention Group

1st ACT Session

- Window open: 1 day post baseline
- Target date: 7 days post baseline
- Window close: 31 days post baseline
- Window length: 30 days

2nd ACT Session

- Window open: 8 days post baseline
- Target date: 14 days post baseline
- Window close: 29 days post baseline
- Window length: 21 days

3rd ACT Session:

- Window open: 15 days post baseline
- Target date: 21 days post baseline
- Window close: 36 days post baseline
- Window length: 21 days

Research Assessment Windows for Intervention and Control Group

Intervention Group 1 Month (4-week) Visit

- Window open: 16 days post first group session
- Target date: 30 days post first group session
- Window close: 90 days post first group session
- Window length: 74 days

Intervention Group 6 Month (24-week) Visit

- Window open: 151 days post first group session
- Target date: 180 days post first group session
- Window close: 240 days post first group session
- Window length: 89 days

Control Group 1 Month (4-week) Visit

- Window open: 16 days post baseline
- Target date: 30 days post baseline
- Window close: 90 days post baseline
- Window length: 74 days

Control Group 6 Month (24-week) Visit

- Window open: 151 days post baseline
- Target date: 180 days post baseline
- Window close: 240 days post baseline
- Window length: 89 days

Windows listed above are used as guides for scheduling visits, but deviations may occur due to participant scheduling.

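### ACT follow-up is timed from the first group session and control follow-up from baseline, so ACT is assessed later after randomisation (7 days if session 1 is on target), and an ACT participant who never attends session 1 has no visit date

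*Combined protocol and SAP*

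**What the plan says.** All references are to the combined protocol and SAP.

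- **Time zero.** Sections 3.1 and 4.5 place randomisation at the baseline visit in both arms.
- **ACT visits (3.5.A).** 1 month: "Target date: 30 days post first group session". 6 months: "Target date: 180 days post first group session".
- **Control visits (3.5.A).** 1 month: "Target date: 30 days post baseline". 6 months: "Target date: 180 days post baseline".
- **Visit windows (3.5.A).** They run from 16 to 90 and from 151 to 240 days after the anchor in both arms. The section calls them scheduling guides from which deviations may occur.
- **Session 1 (3.5.A).** "Target date: 7 days post baseline". The window opens on day 1; "Window close: 31 days post baseline".
- **Sessions 2 and 3 (3.5.A).** Session 2: "Window close: 29 days post baseline". Session 3: "Window close: 36 days post baseline". Section 3.3.A plans the sessions weekly.
- **Start of a group (4.5).** Session 1 waits until five people randomised to ACT are available.
- **Missed sessions (3.6.B Missed Visits, placed within 4.6).** Those who miss session 2 or 3 keep both assessments. Those who miss session 1 move to the next available group; their assessments are not mentioned.
- **Follow-up of everyone.** Section 2.4 expects three assessments in both groups, and section 4.8 follows up all no-shows.
- **Analysis.** Section 8 is intention-to-treat on all randomised participants. Section 8.1 compares binary outcomes by chi-square test and says intra-group correlation will be accounted for. Neither mentions assessment timing.

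**The concern.** The two arms share a time zero at randomisation but are followed on different clocks. The ACT clock starts later, by however long it takes to reach session 1. The windows being guides allows individual deviations, but does not remove a shift built into one arm's schedule.

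Two things are at stake. First, nobody is on ART at entry (section 2.7), and any ART initiation at 6 months is a secondary outcome. If it is counted cumulatively, the arm observed longer has slightly more chance to show it, with no true effect. Second, under intention-to-treat every randomised participant needs a defined assessment. For an ACT participant who never attends session 1, the anchor of both visits does not occur. Control has no such gap, so any resulting missing data would be in one arm only.

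**Working it through.** **1. The plan's own figures.** Window length = close − open: session 1, 31 − 1 = 30; session 2, 29 − 8 = 21; session 3, 36 − 15 = 21; 1 month, 90 − 16 = 74; 6 months, 240 − 151 = 89. All agree with section 3.5.A.

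**2. Visit days after randomisation.** Let s be the day of session 1 after baseline. ACT targets are s + 30 and s + 180; control targets are 30 and 180. The lag is s.

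| s | ACT targets | Control targets | Lag (days) |
|---|---|---|---|
| 1 (window opens) | 31, 181 | 30, 180 | 1 |
| 7 (target) | 37, 187 | 30, 180 | 7 |
| 22 | 52, 202 | 30, 180 | 22 |
| 31 (window closes) | 61, 211 | 30, 180 | 31 |

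Day 22 is the latest start that keeps weekly sessions inside their windows: s + 7 ≤ 29 and s + 14 ≤ 36 both give s ≤ 22. The session-1 window closes two days after the session-2 window, so the two upper limits differ.

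**3. Overlap of the two arms' windows.** At s = 7: 90 − 23 = 67 of 74 days at 1 month, and 240 − 158 = 82 of 89 at 6 months. At s = 22: 90 − 38 = 52 of 74, and 240 − 173 = 67 of 89.

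**4. Effect on ART initiation.** The documents give no expected rate, so the day-180 rate p is assumed, with a constant hazard and no true effect: p(t) = 1 − (1 − p)^(t/180).

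| Assumed p | ACT at day 187 | Gap (points) | ACT at day 202 | Gap (points) |
|---|---|---|---|---|
| 10% | 10.37% | 0.4 | 11.15% | 1.2 |
| 20% | 20.69% | 0.7 | 22.15% | 2.2 |
| 30% | 30.96% | 1.0 | 32.99% | 3.0 |

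With 65 and 35 participants (section 2.4) at 20%, the standard error (SE) of the difference is √(0.2 × 0.8 × (1/65 + 1/35)) = 8.39 points.

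- 7-day lag: 0.69/8.39 = 0.08 SE, or 0.0069 × 65 = 0.45 of a participant.
- 22-day lag: 2.15/8.39 = 0.26 SE, or 0.0215 × 65 = 1.4 participants.
- 31-day lag: 1 − 0.8^(211/180) = 23.02%, so 3.02/8.39 = 0.36 SE.

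**5. Missed session 1.** Thirteen groups over 13 months (sections 2.9 and 3.1) would start about 13 × 30.4/13 = 30.4 days apart if evenly spaced, which is an assumption. Someone who misses a day-7 session would then join at about day 37 and reach session 3 at about day 37 + 14 = 51. Someone who never attends has no s, and hence no visit date if the anchor is the first session attended.

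**6. Time from session 3 to the 6-month visit.** Present target: 180 − 14 = 166 days. If the visit were anchored at baseline: 180 − (s + 14), which is 165 (s = 1), 159 (s = 7), 144 (s = 22), 135 (s = 31) and 129 (s = 37).

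**The case against.** The strongest reply is that the anchor is a reasonable choice. Groups start only when five people are available, and timing from session 1 holds time since the intervention roughly constant. Against windows 74 and 89 days wide, a 7-day shift is small. This stands: the present schedule need not be abandoned.

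The ART calculation also rests on an assumed rate and hazard, and on a questionnaire item whose wording and recall period are not shown. The SE ignores intra-group correlation; positive correlation would make the ratios smaller still. This stands too, so the direction is conditional on a cumulative count.

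A reader might infer three stronger things that the documents do not support.

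- **That ACT is always seen 7 days later.** Seven days applies only when session 1 is on target.
- **That the primary stigma comparison is biased in a known direction.** The relative lag is larger at 1 month (7/30 = 23%, against 7/180 = 4% at 6 months), but nothing in the documents says how the scores move over those days. Satisfaction is asked of ACT participants only (section 5.2), so it has no between-arm timing issue.
- **That non-starters are dropped.** Sections 2.4 and 4.8 show that follow-up of everyone is intended. Only the rule for the date is missing. For someone rebooked, the new group's first session is the natural reading, though it is not written.

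**Conclusion.** The point holds and is minor. As written, ACT assessments fall later after randomisation than control assessments, by the number of days from baseline to session 1, and the analysis section does not address it. If ART initiation is cumulative, the secondary comparison leans towards ACT by 0.4 to 1.0 points at a 7-day lag and 1.2 to 3.0 points at 22 days, for assumed day-180 rates of 10% to 30%. At 20% that is 0.08 and 0.26 SE: small, but in one direction.

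The missing date for ACT participants who never attend session 1 does not depend on those assumptions. The documents give no expected number of non-starters, so its effect cannot be sized.

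**What to change.** 1. **ART comparison.** Keep the present schedule, or align the 6-month visit to baseline if the sponsor prefers. In either case compare ART initiation over a common time from randomisation in both arms, for example to day 151, using first-ART dates. Day 151 is the earliest in-window 6-month visit (control 151; ACT 151 + 1 = 152 at the earliest under the present anchor), so nobody seen in window needs censoring.
2. **Non-starters.** State that an ACT participant who has not attended session 1 by day 31 keeps both assessments on the control windows from baseline (days 16–90 and 151–240). The 1-month visit takes place in what remains of its window, and after session 3 for anyone who joins a later group in time. A day-37 joiner reaches session 3 at about day 51; the limit for weekly sessions is a start by day 90 − 14 = 76.
3. **Reporting.** Give days from randomisation to each assessment by arm. Treat any analysis of stigma scores adjusted for that time as descriptive only, because it is a post-randomisation variable partly determined by arm.

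**Cost.** A first-ART date field if the questionnaires lack one, an amended window text and scheduling rule, and a little extra analysis. Stopping at day 151 leaves out later starts: at the assumed 20%, 1 − 0.8^(151/180) = 17.1% would be counted. If the 6-month visit is re-anchored, the interval from session 3 is no longer fixed at a 166-day target. It becomes 165 to 135 days for session 1 on days 1 to 31, and about 129 for a day-37 joiner. That is a real loss for the 6-month exploratory scales, and is why re-anchoring is left as an option.
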